10.2.2 Documentation and Monitoring Adverse Events

All AEs encountered during the clinical trial following subject consent through the last study visit will be recorded on the appropriate Adverse Events case report form (eCRF).

Special considerations:

- Elective procedures or routinely scheduled treatments are not considered AEs. However, an untoward medical event occurring in association with a prescheduled elective procedure should be recorded as an AE.
- A baseline condition is not considered an AE unless the condition worsens following study drug administration.
- Death itself is not considered an AE; it is, instead, the outcome of an AE.
- SAEs that are considered related (i.e., determined to be possibly, probably, or definitely related) to sofspironium bromide by the Investigator or Sponsor should be followed until the event resolves or stabilizes (see [Section 10.3.1](#)).

10.2.3 Assessment of Adverse Events

For each reported AE, the start and resolution dates, intensity, seriousness (i.e., whether the event meets the definition of an SAE [[Section 10.3.1](#)]), relationship of the event to the study drug, action taken regarding study drug, and outcome of the event will be documented on the eCRF.

Intensity

The following definitions should be used to assess and grade AE intensity, including laboratory abnormalities judged to be clinically significant.

Severity	Grade	Description
Mild	1	Awareness of sign or symptom, but easily tolerated
Moderate	2	Discomfort enough to cause interference with usual activity
Severe	3	Incapacitating with inability to work or do usual activity

Note: a severe AE is not necessarily serious.

Relationship

The relationship of a reported AE to study drug should be assessed using the guidelines presented in the following table.

Degree of Certainty	Description
Definitely Related	An event that follows a reasonable temporal sequence from administration of the test article; that follows a known or expected response pattern to the test article; and that is confirmed by improvement on stopping or reducing the dosage, and reappearance of the event on repeated exposure (re-challenge).
Probably Related	An event that follows a reasonable temporal sequence from administration of the test article; that follows a known or expected response pattern to the test article; and that is confirmed by improvement on stopping or reducing the dosage of the test article; and that is unlikely to have been caused by concurrent/underlying illness or other drugs, procedures, or other causes.
Possibly Related	An event that follows a reasonable temporal sequence from administration of the test article; that follows a known or expected response pattern to the test article; but may have been caused by concurrent/underlying illness, other drug, procedure, or other causes.
Unlikely Related	An event that does not follow a reasonable temporal sequence from administration of the test article; that does not follow a known or expected response pattern to the test article, or most likely was caused by concurrent/underlying illness, other drug, procedure, or other causes, because of their known effects.
Not related	An event almost certainly caused by concurrent/underlying illness, other drug, procedure, or other causes.

Outcome

Each AE will be characterized according to the outcomes described in the following table.

Outcome	Description
Recovered/Resolved	The subject has fully recovered from the event with no observable residual effects.
Recovering/Resolving	The effects of the event are improving, or events have stabilized (are constant and not expected to improve or worsen) but have not returned to baseline.
Not recovered/Not Resolved	The effects of the event are still present and changing. The event is not considered stabilized or resolved.
Recovered/Resolved with Sequelae	The subject has fully recovered from the event with some observable residual effects.
Fatal	The event was the primary cause of death (may or may not be the immediate cause of death).
Unknown	The event outcome is unknown.

Death is an outcome of an event and not an event per se. Sudden death or death due to unexplainable cause(s) is to be reported, but follow-up will be pursued until cause of death is determined.

Action Taken with Study Drug

Action taken with study drug in relation to each AE will be characterized as follows:

- None
- Drug withdrawn
- Drug interrupted
- Unknown
- Not applicable

- Other (specify on eCRF)

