1.3 Risk / Benefit Assessment

The results to date of the clinical program support the safe use of sofspironium bromide gel, 15% for the treatment of primary axillary hyperhidrosis. Ten clinical studies have been conducted with sofspironium bromide gel exposing over 700 adult subjects to the active ingredient: two Phase 1 studies in healthy adults, four Phase 1 and three Phase 2 studies in adults with primary axillary hyperhidrosis, and a Phase 2 study in adults with primary palmar hyperhidrosis.

Sofspironium bromide has consistently demonstrated low incidence of treatment-emergent adverse events (TEAEs) following daily application for periods of time up to 6 weeks. Most AEs have been mild and transient, with all resolving after treatment discontinuation. A long-term safety study (BBI-4000-CL-303) to evaluate the safety and tolerability of sofspironium bromide gel, 15% in subjects ≥ 12 years of age has been initiated and is ongoing at this time.

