10.2 Adverse Events

10.2.1 Definition of Adverse Events

According to the Code of Federal Regulations, 21 CFR Parts 312.32 and 320.32 (IND Safety Reporting, Applicability of requirements regarding an "Investigational New Drug Application"), FDA Guidance for Industry (Investigational New Drug Safety Reporting Requirements for Human Drug and Biological Products and Safety Reporting Requirements for Bioavailability and Bioequivalence Studies in Humans) (Federal Register/Vol. 75, No. 188/September 29, 2010) and ICH E2A (Clinical Safety and Data Management: Definitions and Standards for Expedited Reporting):

- An AE means any untoward medical occurrence associated with the use of a drug in humans, whether or not considered drug related.
- A suspected drug-related adverse reaction means any AE for which there is a reasonable possibility that the drug caused the AE.

The following information should be considered when determining whether to classify a test result, medical condition, or other incident as an AE:

- Adverse events will be recorded from the time of informed consent.
- Abnormal laboratory values should not generally be recorded as an AE unless an intervention is required, the laboratory abnormality is associated with clinical signs or symptoms, or the lab abnormality results in study termination or interruption/discontinuation of study treatment. When recording an AE resulting from a laboratory abnormality, the resulting medical condition rather than the abnormality itself should be recorded (e.g., record "anemia" rather than "low hemoglobin").

- Complications that occur in association with a protocol-mandated intervention (e.g., invasive procedures such as biopsies) should be recorded as AEs.
- Whenever possible, the Investigator should group signs or symptoms that constitute a single diagnosis under a single event term. For example, cough, rhinitis, and sneezing might be grouped together as “upper respiratory tract infection”. If possible, abnormal laboratory results that meet the definition of an AE (see above) should be reported as a clinical diagnosis rather than the abnormal value itself (e.g., “anemia” rather than “decreased blood count”).

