### 13.3 Primary Analyses

#### 13.3.1 Safety

Safety evaluations will consist of AEs, application site local tolerability, physical examinations, vital signs, ECGs, and laboratory measurements (hematology, chemistry, and urinalysis).

- Adverse events:
  - Adverse events will be mapped to standard terms, i.e., MedDRA System Organ Class and Preferred Term.
  - Adverse events that occurred during the screening period will be listed separately and will not be included in the AE tabulations.
  - Adverse events that start on or after first dose will be considered a TEAE. At each post-baseline visit, the number and proportion of subjects reporting any given TEAE will be tabulated by severity; each subject will be counted only once according to the worst severity reported up to the current visit. Separate tables will be constructed for (a) all reported TEAEs, (b) protocol treatment related TEAEs, (c) serious TEAEs, and (d) TEAEs leading to protocol treatment discontinuation.
- At each applicable visit, local tolerability (burning, itching, stinging, scaling, and erythema at either axilla) will be described by severity as defined in Appendix E. Subject and Investigator assessments will be included in separate tables and listings, with the count and percentage of subjects within each severity (maximum severity assessed at either axilla) presented by parameter and visit.
- Vital signs will be summarized similarly as for laboratory parameters but without shift tables.
- Laboratory parameters will be descriptively summarized (mean, SD, median, minimum, maximum) for values at each visit and for changes from baseline at each subsequent visit. In addition, at each post baseline visit, parameter status (low, normal, high) will also be summarized as shift tables vs. baseline status.
- Descriptive statistics and/or frequency tables will be prepared as appropriate for physical examinations, and ECG (HR, QTcF, PR, and QRS) parameters, and abnormalities (e.g., normal; abnormal, not clinically significant; abnormal, clinically significant).
- Concomitant medications will be mapped according to the World Health Organization Drug Dictionary (WHODD) and will be presented in data listings.

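### Read literally, the AE relationship table makes a recognised response pattern a condition of every related grade, so a reaction of a truly new kind may be under-counted as drug-related

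*Protocol*

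**What the plan says.** The relationship table in Protocol 10.2.3 has five grades, introduced as guidelines. The upper three each join a pattern condition to reasonable timing:

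- Definitely Related: "that follows a known or expected response pattern to the test article; and that is confirmed by improvement on stopping or reducing the dosage", plus recurrence on re-exposure.
- Probably Related: "known or expected response pattern to the test article; and that is confirmed by improvement on stopping or reducing the dosage of the test" article, plus no likely alternative explanation.
- Possibly Related: "follows a known or expected response pattern to the test article; but may have been caused by concurrent/underlying illness" or another listed cause.

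Unlikely Related is the only grade that mentions an unfamiliar pattern. After a clause on poor timing and a semicolon it continues: "that does not follow a known or expected response pattern to the test article, or most likely was caused by concurrent/underlying illness". Not Related is for an event almost certainly due to something else.

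Protocol 10.2.1 defines a suspected drug-related reaction as "any AE for which there is a reasonable possibility that the drug caused the AE", with no pattern condition. Protocol 10.2.2 treats an SAE as related when it is "determined to be possibly, probably, or definitely related".

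Relationship to study drug is part of a primary safety endpoint (Protocol 3.2.1.1, SAP 7.2.1.1). SAP 13.3.1 plans four AE tables, one of them "b) protocol treatment related TEAEs", but does not say which grades enter it.

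**The concern.** Causality and expectedness are separate questions, and the table makes the first depend on the second. An investigator who follows it has no related grade for an event that begins at a plausible time and has no better explanation but is of a kind not previously recognised.

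That matters more here than in a late confirmatory trial. Protocol 1.3 describes earlier experience in over 700 adults, with a low TEAE incidence "following daily application for periods of time up to 6 weeks". The preceding paediatric study lasts about 7 days, and the long-term study in subjects aged 12 and over is still running. This study treats ages 9 to 17 for up to 24 weeks, so recognising something new is part of its purpose.

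Two things depend on the grade. One is the related-TEAE table. The other is the set of duties confined to related SAEs: follow-up until resolved or stable (10.2.2, 10.3.1, 10.4) and reporting of SAEs that arise after study completion (10.3.1).

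**Working it through.** The plan has no figure to reproduce here. The maximum of 24 subjects is carried over from Study BBI-4000-CL-105, not calculated. The check is one of logic.

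**Inputs (Protocol 10.2.3).** T = reasonable timing; P = recognised pattern; D = improvement on stopping or reducing; R = recurrence on re-exposure; A = standing of another cause (unlikely, may, most likely, almost certain).

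- Definitely = T and P and D and R
- Probably = T and P and D and (A = unlikely)
- Possibly = T and P and (A = may)
- Unlikely, clauses joined by *and* = (not T and not P) or (A = most likely)
- Unlikely, clauses joined by *or* = not T or not P or (A = most likely)
- Not Related = (A = almost certain)

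**Event of a new kind with good timing.** Set T = yes and P = no. The rest gives 2 × 2 × 4 = 16 combinations.

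| Other cause | Combinations | Any related grade | Unlikely read as *and* | Unlikely read as *or* |
|---|---|---|---|---|
| unlikely | 4 | 0 | no grade | Unlikely |
| may | 4 | 0 | no grade | Unlikely |
| most likely | 4 | 0 | Unlikely | Unlikely |
| almost certain | 4 | 0 | Not Related | Unlikely and Not Related |

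No combination reaches a related grade, even with D and R both positive and no other cause. Under *and*, 8 of 16 fit no grade, 4 are Unlikely and 4 are Not Related. Under *or*, all 16 are Unlikely and 4 of them are also Not Related. These are counts of logical cases, not probabilities. The 8 in the first two rows are the ones where a drug cause is a serious candidate.

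**Expected pattern, drug continued.** Set T = yes, P = yes, D = no, A = unlikely. Definitely and Probably fail on D. Possibly fails as worded because it supposes that something else may be the cause. Unlikely fails on both readings, and Not Related fails. The event has no clean grade.

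**Scale, with assumed true rates p.** The chance that at least one of 24 subjects has a given new reaction is 1 − (1 − p)^24:

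- p = 2%: 1 − 0.98^24 = 38%
- p = 5%: 1 − 0.95^24 = 71%
- p = 10%: 1 − 0.90^24 = 92%

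One subject moved out of the related table changes its proportion by 1/24 = 4.2 percentage points. As an illustration only, if 3 of 24 subjects (12.5%) had such a reaction and grading were strictly literal, the related table would show 0 of 24.

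**The case against.** A reader might infer that a new paediatric or long-term reaction cannot be counted as drug-related at all. The documents do not support that.

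- The table is offered as guidelines, and 10.2.1 gives investigators a reasonable-possibility standard. Under 10.2.2 and 10.4 either the Investigator or the Sponsor may consider an SAE related.
- A new age group or a later week is not in itself a new response pattern. The drug is described as an anticholinergic, and Appendix F already lists local skin effects. Such an effect first appearing in a 10-year-old, or after week 6, can still be an expected pattern. The term is undefined and is not tied to adult experience.
- The semicolon in Unlikely Related can be read as joining its clauses. A new kind of event is then left ungraded and open to judgement, not directed to Unlikely.
- Possibly Related asks only that some other cause may explain the event, and its list of causes is open-ended. Many investigators would use it for the second gap.

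A reader might also infer that such events disappear or go unfollowed. They do not. All AEs are recorded, and SAP 13.3.1 plans tables of all TEAEs, serious TEAEs and TEAEs leading to discontinuation, none of which uses the grade. SAEs during the study go to the Sponsor within 24 hours regardless of causality (10.3.1). Section 7.5 schedules visits every 7 to 14 days for AEs unresolved at Visit 8, whatever their cause. The SAP's preliminary output list names no all-TEAE table, but that does not cancel the requirement in the SAP text.

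These points limit the consequence. They do not remove the conflict between 10.2.1 and 10.2.3. Whether a new kind of event counts as related is left to whether each investigator departs from the table.

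**Conclusion.** The concern holds as a wording conflict with a bounded effect. Taken literally, 10.2.3 gives no related grade to a reaction of a truly new kind, and no clean grade to an expected-pattern event without improvement on stopping or an evident other cause. Both conflict with the reasonable-possibility definition in 10.2.1.

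The likely result is under-counting in the related-TEAE table, which serves a primary safety endpoint, and in the duties limited to related SAEs. The number of events affected cannot be estimated from the documents. It depends on whether any new kind of reaction occurs and on how literally sites apply the table. The 0-of-24 figure follows from assuming both three such reactions and strictly literal grading, so it forecasts nothing. Overall AE incidence, the all-TEAE table and the sample size are unaffected.

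**What to change.** In Protocol 10.2.3:

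1. Define Possibly Related as reasonable timing and a reasonable possibility of drug cause, matching 10.2.1, whether or not another cause is also possible.
2. Remove the response-pattern clause from Unlikely Related.
3. In Probably and Definitely Related, make the pattern supporting evidence, not a requirement.

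In SAP 13.3.1, state that related TEAEs are those graded possibly, probably or definitely related, as Protocol 10.2.2 already does for SAEs.

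With these changes, the 8 combinations in which another cause is unlikely or merely possible become at least Possibly Related whenever a drug cause is reasonably possible. So does the expected-pattern event in a subject who keeps applying the drug. The ambiguity in Unlikely Related goes with its pattern clause.

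The cost is an edit to one protocol table, the eCRF completion guide and one SAP sentence. A few more events may be graded Possibly Related, so the related-TEAE rate may be slightly higher.

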10.3 Serious Adverse Events

Any AE that is serious (see definition below) and occurs after administration of study drug must be reported to the Sponsor within 24 hours of discovery of the event. An event occurring after informed consent but before administration of study drug that is considered serious and possibly related to a protocol procedure must also be reported to the Sponsor within 24 hours of discovery of the event.

10.3.1 Definition and Reporting Procedures

An AE should be classified as an SAE if it meets one of the following criteria.

Fatal:	The AE resulted in death.
Life Threatening:	The AE placed the patient at immediate risk of death. This classification does not apply to an AE that hypothetically might cause death if it were more severe.
Hospitalization:	The AE required or prolonged an existing inpatient hospitalization. Hospitalizations for elective medical or surgical procedures or treatments planned before the signing of informed consent in the study or routine check-ups are not serious AEs by this criterion. Hospitalizations or prolonged hospitalizations for scheduled therapy need not be captured as SAEs.
Disabling/Incapacitating:	Resulted in a substantial and permanent disruption of the patient's ability to carry out activities of daily living.
Congenital Anomaly or Birth Defect:	An adverse outcome in a child or fetus of a patient exposed to the study drug or study treatment regimen before conception or during pregnancy.
Medically Significant:	The AE did not meet any of the above criteria but could have jeopardized the patient and might have required medical or surgical intervention to prevent one of the outcomes listed above.

Every SAE (regardless of suspected causality) should be reported to the Sponsor within 24 hours of discovery of the event. The processes for reporting and documenting SAEs are provided in the study manual. Investigators are responsible for reporting these events to their IRB/IEC in accordance with federal and institutional laws and regulations.

Additional updates from the Investigator may be necessary as more information becomes available on the SAE, and all treatment-related SAEs will be followed until the acute event has resolved or stabilized, even if the subject discontinues study participation prior to the SAE resolution. Any new information or follow-up information pertaining to previously reported SAEs will be reported to the Sponsor within 24 hours of becoming aware of the new or follow-up information. The new or follow-up information should be faxed to the Sponsor at [name] or emailed to [contact].

Any SAE that occurs after study completion and is considered by the Investigator to be related to sofpironium bromide, should be reported to the Sponsor.

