10.3.2 Reporting Serious Adverse Events to Regulatory Agencies

The Sponsor will determine which SAEs qualify for expedited reporting to regulatory agencies. SAEs that qualify for expedited reporting will be submitted to regulatory agencies in accordance with applicable federal regulations.

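### The SAE disability criterion requires permanence, so a substantial but reversible incapacity that meets no other criterion is not an SAE

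*Protocol*

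**What the plan says.** Protocol 10.3.1 lists six criteria, and meeting one is enough. Four matter here:

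- **Disabling/Incapacitating:** "Resulted in a substantial and permanent disruption of the patient's ability to carry out activities of daily living".
- **Life Threatening:** "The AE placed the patient at immediate risk of death".
- **Hospitalization:** "The AE required or prolonged an existing inpatient hospitalization".
- **Medically Significant:** an event that meets none of the others but "could have jeopardized the patient and might have required medical or surgical intervention to prevent one of the outcomes listed above".

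The other two are death and congenital anomaly or birth defect.

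Protocol 10.2.3 ties the seriousness field on the eCRF to this definition. It grades intensity separately on a three-level scale and notes that a severe event need not be a serious one. The SAP has no seriousness definition of its own.

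Several steps depend on SAE status. Under Protocol 10.3 a serious AE occurring after study drug "must be reported to the Sponsor within 24 hours of discovery of the event", and 10.3.1 repeats the duty: "Every SAE (regardless of suspected causality) should be reported to the Sponsor within 24 hours of discovery of the event". Protocol 10.3.2 adds: "The Sponsor will determine which SAEs qualify for expedited reporting to regulatory agencies". SAP 13.3.1 calls for separate tables of (a) all TEAEs, (b) related TEAEs, (c) serious TEAEs and (d) TEAEs leading to discontinuation of treatment. Appendix A of the SAP numbers the serious-TEAE table 14.3.1.2.

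**The concern.** Long-term safety in children and adolescents is a primary objective of this extension. The disability criterion should pick out an event that leaves a child unable to carry on normal daily life, but as written it does so only when the loss never reverses.

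Protocol 1.3 reports that AEs so far, in adults treated for up to 6 weeks, were mostly mild and all resolved after treatment stopped. If that pattern carries over to children, a drug-related incapacity would be reversible, and this criterion would hardly ever apply to one. The same history suggests that such an incapacity would be uncommon.

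At stake are prompt notice to the sponsor, consideration for expedited reporting, and visibility in the one AE table reserved for serious events.

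**Working it through.** No arithmetic applies, and the plan gives no figure to reproduce. The check is to follow one kind of event through the definition and then through everything that depends on it.

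**Event.** A hypothetical child is, for some weeks, substantially unable to manage ordinary daily activities. The child is looked after at home, is never at immediate risk of death, needs no intervention to prevent anything worse, and recovers fully.

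**Step 1: the six criteria of Protocol 10.3.1.**

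| Criterion | Met? | Reason |
|---|---|---|
| Fatal | No | The child survives |
| Life threatening | No | No immediate risk of death |
| Hospitalization | No | No inpatient admission |
| Disabling/incapacitating | No | Substantial, but not permanent |
| Congenital anomaly | No | Not applicable |
| Medically significant | No | No possible need for intervention to prevent a listed outcome |

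The event meets 0 of 6 and is not an SAE. Without the permanence condition it would meet 1 of 6 and be an SAE.

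**Step 2: can the residual criterion close the gap?** Only in part. Medically significant has no permanence test of its own. Its test is whether intervention might have been needed to prevent one of the listed outcomes. Those include hospitalization and immediate risk of death, so a reversible incapacity that might have needed treatment to avoid admission can qualify, by judgement. The disability outcome on that list is the permanent one, however, so preventing a reversible incapacity is not itself a qualifying reason.

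**Step 3: can the intensity grade close it?** No. Grade 3 in Protocol 10.2.3 describes incapacitating events, but the note beneath the scale keeps severity apart from seriousness.

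**Step 4: what follows from not being an SAE.**

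- The 24-hour duty in Protocol 10.3 and 10.3.1 does not apply.
- The event is not among those the sponsor considers under Protocol 10.3.2.
- The eCRF seriousness field is negative, so the event is absent from table (c) in SAP 13.3.1.

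**Step 5: what survives.**

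- The event is recorded as an AE with its intensity, relationship, action taken and outcome (Protocol 10.2.3).
- SAP 13.3.1 places it in table (a) by severity, in (b) if related and in (d) if treatment is stopped.
- It appears in Listing 16.2.7.1. Table (a) is not yet on the preliminary list in SAP Appendix A, but the SAP text specifies it.

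**The case against.** The strongest reply is that the gap is very small. To fall into it, a child must be substantially incapacitated and yet not be admitted, not be in immediate danger, and not possibly need intervention to avoid a listed outcome. The wording of medically significant is permissive. Other safeguards also apply:

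- The investigator must review AEs promptly, and safety assessments are to reach the EDC system within 48 hours if possible (Protocol 4.6.2).
- The Study Review Committee, which includes the sponsor's and CRO's medical monitors, helps identify safety concerns (4.6.1).
- Dosing must stop when the investigator or the committee judges continuation an unnecessary risk (4.5.1.1).

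All of this stands as a limit on size. None of it makes the event an SAE.

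A second reply is that nothing in the documents shows the permanence condition to be an error. Protocol 10.2.1 names 21 CFR 312.32 and ICH E2A, and a reader might infer that 10.3.1 departs from them. Neither document reproduces their text on seriousness, so that inference is not available here. The point rests only on the protocol's own wording and what depends on it, and is best described as a design choice worth changing.

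A reader might also argue that permanence cannot be known within 24 hours of discovery. That may often be so, but the documents do not say it and the conclusion does not need it.

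Finally, "The processes for reporting and documenting SAEs are provided in the study manual". The manual is not available here. Protocol 10.2.3 refers the seriousness field to 10.3.1, not to the manual.

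**Conclusion.** The point holds in a limited form. Followed exactly, Protocol 10.3.1 leaves a substantial but reversible incapacity that meets no other criterion outside the 24-hour report, the expedited-reporting pool and table (c).

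The size cannot be put as a number. The documents give no rate for such events, and among at most 24 subjects there may be none.

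Two stronger readings are tempting and are not supported:

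- **That reversible incapacity can never be serious.** It can, through admission, immediate risk of death or medical significance, none of which has its own permanence test.
- **That the event drops out of the safety analysis or distorts a primary endpoint.** The listed safety endpoints cover AE incidence, severity, relationship and discontinuation due to an AE. Seriousness is not among them, and the event still counts toward the all-TEAE table.

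The conclusion assumes that investigators apply the criterion as written and that no unseen document substitutes a broader one. The change is worth making because it costs little and bears on prompt safety reporting in children.

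**What to change.** In Protocol 10.3.1, replace the disabling/incapacitating criterion with:

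*Resulted in a persistent or significant incapacity or a substantial disruption of the patient's ability to carry out normal activities of daily living; it need not be permanent.*

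Leave the wording of the other five criteria alone. No exception for Grade 3 intensity is needed, because the existing note in 10.2.3 already prevents a severe grade alone from making an event serious. The SAP needs no change, since table (c) follows the seriousness classification.

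The cost is one reworded sentence, any matching text in the study manual, and the IRB/IEC approval that Protocol 13.1 requires for an amendment. Because medically significant refers back to the listed outcomes, it widens slightly as well. The likely effect is at most a few more SAE reports among no more than 24 subjects. Investigators will still have to judge what is significant or substantial; only the permanence test goes.
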